14.7 CYP3A4 and CYP1A2 Inhibitors/Inducers

<http://medicine.iupui.edu/clinpharm/ddis/>

Strong inhibitors and inducers (underlined) are not permitted during this study.

CYP3A4 inhibitors

indinavir
nelfinavir
ritonavir
saquinavir
clarithromycin
itraconazole
ketoconazole
nefazodone (withdrawn in the US)
erythromycin
grapefruit juice
verapamil
diltiazem
cimetidine
amiodarone
fluvoxamine
mibepradil (withdrawn in the US)
troleanandomycin

CYP3A4 inducers

rifampin
carbamazepine
phenobarbital
phenytoin
pioglitazone
rifabutin
St. John's wort

Sponsor's code: ACTION
 EudraCT No: 2019-004991-20
 Version: 4.0
 Date: 15 July 2021
 CONFIDENTIAL

14.8 CLINICAL STUDY SAE REPORT FORM

| | |
|---|---|
| Associated Procedure / Instruction Ref: | 080493 - Expedited & Periodic Reporting of Suspected Unexpected Serious Adverse Reactions |
| Version: 9.0 | Effective date: 15-Dec-2019 |

Clinical Study SAE Report Form

Please complete as many details as possible and forward it to IPSEN contact immediately/within 24 hours

(please choose one): Initial Follow Up Follow-up No.: _____

Email to: [contact]

| PROTOCOL | SITE | SUBJECT NUMBER | COUNTRY |
|----------|-------|----------------|---------|
| _____ | _____ | _____ | _____ |

A - SUBJECT INFORMATION

Birth Date

| | | | | |
|--|--|--|--|--|
| | | | | |
|--|--|--|--|--|

 Height (cm)

| | | |
|--|--|--|
| | | |
|--|--|--|

 Weight (kg)

| | | | |
|--|--|--|--|
| | | | |
|--|--|--|--|

 Sex : M F

Day Month Year

Age: _____ years

Race (if applicable): Asian Black or African American White Native Hawaiian or Other Pacific Islander American Indian or Alaska Native

Other Specify: Not Applicable

Pregnant? Yes No Not Applicable If Yes, please complete Standard Pregnancy Outcome Report Form (Form No.080479)

Pregnancy in participant's partner? Yes No Not Applicable

B - SERIOUS ADVERSE EVENT DESCRIPTION (e.g. Diagnosis of SAE(s). If diagnosis is not known, describe symptom(s) in free text section below)

| | | | | | | | | | | | | | | | | | | | | | | |
|---|---|---|--|--|--|--|--|--|--|--|--|--|--|--|--|--|--|--|--|--|--|--|
| Serious Adverse Event | | | | | | | | | | | | | | | | | | | | | | |
| Intensity OR Grade (1-5 for NCI-CTCAE) |  Mild  Moderate  Severe | Oncology studies - National Cancer Institute Common Toxicity Criteria (NCI - CTCAE) Grade Grade 1-5: _____ | | | | | | | | | | | | | | | | | | | | |
| Seriousness Criteria (Tick all that apply) (DD MM YYYY) |  Resulted in death If yes, Cause of death: Date of Death: 

 	 	 	 	 	 	 	

  Congenital abnormality or birth defect  Persistent or significant disability / incapacity  Requires or prolongs hospitalization If yes, Admission Date: 

 	 	 	 	 	 	

 Discharge Date: 

 	 	 	 	 	 	

  Life-threatening  Important Medical Event | | | | | | | | | | | | | | | | | | | | | |
| | | | | | | | | | | | | | | | | | | | | | | |
| | | | | | | | | | | | | | | | | | | | | | | |
| | | | | | | | | | | | | | | | | | | | | | | |
| Other suspicious causes |  Yes  No If Yes, please complete the information below  Disease related  Other Medical condition i.e. Other than disease related (See section E)  Procedure related to protocol  Concomitant medication (see Section G)  Unscheduled procedure  Other (specify) | | | | | | | | | | | | | | | | | | | | | |
| INVESTIGATOR NAME: | DATE: | | | | | | | | | | | | | | | | | | | | | |
| INVESTIGATOR SIGNATURE: | | | | | | | | | | | | | | | | | | | | | | |

3 LIST OF ABBREVIATIONS

ADO	Available Data Only
AE	Adverse Events
AESI	Adverse Event of Special Interest
ATC	Anatomical Therapeutic Chemical
BCLC	Barcelona Clinic Liver Cancer
CI	Confidence Interval
CIBEREHD	Centro de Investigación Biomédica en Red Enfermedades Hepáticas y Digestivas
CRF	Case Report Form
CTCAE	Common Terminology Criteria for Adverse Events
DSMB	Data Safety Monitoring Board
ECG	Electrocardiogram
FACT-HEP	Functional Assessment of Cancer Therapy – Hepatobiliary cancer
HCC	Hepatocellular Carcinoma
ICH	International Conference on Harmonization
ICMDM	Institut Clínic de Malalties Digestives i Metabòliques
IDIBAPS	Institut d'investigacions Biomèdiques August Pi i Sunyer
LSM	Leas Square Means
MAR	Missing At Random
MedDRA	Medical Dictionary for Regulatory Activities
MMRM	Mixed Models for Repeated Measurements
ORR	Objective Response Rate
OS	Overall Survival
PEP	Primary endpoint
PP	Per protocol
PPS	Post-progression survival
PT	Preferred Term
SAE	Serious Adverse Event
SAP	Statistical Analysis Plan
SE	Standard Error
SD	Standard Deviation
SCReN	Spanish Clinical Research Network
TTP	Time to progression
VAS	Visual Analogical Scale

4 SCOPE OF ANALYSIS PLAN

The statistical analysis will be carried out in accordance with the principles specified in the International Conference on Harmonization (ICH) Topic E9 (CPMP/ICH/363/96)¹. This SAP will follow the general regulatory recommendations given in the ICHE9¹ guidance, as well as other specific guidance on methodological and statistical issues². Also, it will stick to the recommendations given by the consensus documents of the scientific journals^{3,4,5} to improve reliability and value of medical research literature by promoting transparent and accurate reporting of clinical research studies.

5 SOFTWARE METHODS

All tables and listings will be produced using SAS System⁶ (Release 9.4 or an upgraded version) and will be presented in WinWord documents.

6 STUDY OBJECTIVES

6.1 PRIMARY OBJECTIVES

The aim of this study will be to test the safety of cabozantinib in patients sorafenib intolerant according to the RESORE trial⁷ definition and in patients treated with first-line treatments other than sorafenib. Indeed, although a phase III trial (CELESTIAL)⁸ showed improved OS with acceptable toxicity in sorafenib intolerant patients or in those who progressed on sorafenib, no clear definition was applied to identify those patients. The **primary endpoints** are the rate and type of AEs leading to treatment discontinuation, the rate and type of AEs, serious AEs (SAEs), rate of related-AE and rate of death.

6.2 SECONDARY OBJECTIVES

Secondary endpoints are time to progression, pattern of progression, overall survival, post-progression survival, rate of patients who develop new extra-hepatic spread and ORR. Radiologic tumor response will be defined according to the RECIST 1.1⁹ and then will be evaluated by BCLC-RECIST¹⁰.

6.3 EXPLORATORY OBJECTIVES

Exploratory objectives are:

- To evaluate the role of tissue biomarkers (see section 7.7 for timing-points) in determining the antitumoral activity of cabozantinib.
- To describe the quality of life.
- The gut microbiota composition at different time points.

This study will collect blood and biopsy samples but the exploratory objectives will be done in a second study only if the study meets the safety end-point.

7 TRIAL CHARACTERISTICS

7.1 STUDY DESIGN

The study is a prospective, multicenter, open-label, non-controlled phase IIa study evaluating cabozantinib for the treatment of patients with unresectable hepatocellular carcinoma sorafenib intolerant according to the RESORCE trial definition or who received other first-line treatments than sorafenib. Treated patients will be followed until death, withdrawal of consent or until the end of the duration of the study.

7.2 STUDY TREATMENTS

In this protocol investigational products is cabozantinib.

See protocol section 6.1 for more information about dose modification rules for the study treatment.

7.2.1 Cabozantinib

Cabozantinib will be initiated at full dose (60 mg/day) and the dose will be modified upon development of adverse events according to the manufacturer's recommendations and continued until symptomatic tumor progression, unacceptable adverse events, patient decision or death.

7.3 DISCONTINUATION OF THE STUDY

7.3.1 End of study

After discontinuation from study therapy, there is 1 follow-up visit required within seven days of discontinuation (on site visit), and additional survival follow-up (on-site or phone visits). The study will end when survival follow-up collection has concluded. The last visit will be defined as the latest follow-up Visit. Additional survival follow-up may continue beyond the time of this analysis.

7.3.2 Discontinuation of cabozantinib

Subjects MUST discontinue study medication:

- Withdrawal of informed consent (subject's decision to withdraw for any reason)
- Any clinical AE, abnormal laboratory test results or any illness which, in the opinion of the investigator, indicates that continued participation in the study is not in the best interest of the subject.
- Clinical deterioration (see protocol section 6.1.7 for more details)
- Pregnancy
- Termination of the study by the promoter
- Specific criteria for discontinuation of outlined in (see protocol section 6.1.6 for more details)
- Loss of ability to freely provide consent through imprisonment or involuntary incarceration for treatment of either a psychiatric or physical (eg, infectious disease) illness.
- Protocol defined disease progression unless subject is eligible for treatment beyond progression (see protocol section 6.1.7.1 for more details).
- In the case of pregnancy, the investigator must immediately notify the Medical Monitor/designee of this event. In most cases, the study drug will be permanently discontinued in an appropriate manner. If the investigator determines a possible favorable benefit/risk ratio that warrants continuation of study drug, a discussion between the investigator and the Principal Investigator must occur.
- All subjects who discontinue should comply with protocol specified follow-up procedures as outlined in section. The only exception to this requirement is when a subject withdraws

consent for all study procedures or loses the ability to consent freely (ie, is imprisoned or involuntarily incarcerated for the treatment of either a psychiatric or physical illness). If a subject was withdrawn before completing the study, the reason for withdrawal must be entered on the appropriate CRF page.

7.3.3 Post study drug study follow-up

In this study, overall survival is a secondary endpoint. Subjects who discontinue study drug must continue to be followed for collection of survival follow-up data until death or the conclusion of the study. Survival follow-up visits should be planned every 3 months from Follow-Up Visit-1 and may be performed by phone contact or office visit.

7.3.4 Withdrawal of consent

Subjects who request to discontinue study treatment will remain in the study and must continue to be followed for protocol specified follow-up procedures. The only exception to this is when a subject specifically withdraws consent for any further contact with him/her or persons previously authorized by subject to provide this information. Subjects should notify the Investigator of the decision to withdraw consent from future follow-up in writing, whenever possible. The Investigator should explain the withdrawal of consent in detail in the medical records, as to whether the withdrawal is from further treatment with study drug only or also from study procedures and/or post treatment study follow-up, and entered on the appropriate CRF page.

7.3.5 Lost to follow-up

All reasonable efforts must be made to locate subjects to determine and report their ongoing status. This includes follow-up with persons authorized by the subject as noted above. Lost to follow-up is defined by the inability to reach the subject after a minimum of three documented phone calls, faxes, or emails or whatsapp messages as well as lack of response by subject to one registered mail letter. All attempts should be documented in the subject's medical records. If it is determined that the subject has died, the site will use permissible local methods to obtain the date and cause of death. If after all attempts, the subject remains lost to follow-up, then the last known alive date as determined by the investigator should be reported and documented in the subject's medical records.

7.4 JUSTIFICATION OF SAMPLE SIZE

The sample size calculation will be triggered by the primary outcome, i.e, the rate of adverse events (AE) with CTCAE ≥ 3 excluding palmar-plantar erythrodysthesia (critical AEs). The expected rate for this outcome was 56% in this population^{Error! No se encuentra el origen de la referencia.}. The Simon's two-stage optimal design¹¹ will be used to test the alternative hypothesis that with cabozantinib the rate of critical AEs will be reduced at least to 32.5% against the null hypothesis of 56% as previously observed. In the first stage, 14 patients will be accrued. If there are 8 or more critical AES in these 14 patients, the study will be stopped because of futility. Otherwise, 26 additional patients will be accrued for a total of 40. The null hypothesis will be rejected if 23 or fewer critical AEs are observed in 40 patients. This design yields a type I error rate of 2.5% one-sided and power of 80% when the true response rate is 67.5%.

All patients exposed to the study treatment (regardless of protocol adherence) will count be safety, and thus no need to sample size increases as per potential withdrawals are foreseen.

7.5 INTERIM ANALYSES

We plan to conduct 1 fixed pre-scheduled interim analyses for futility as per the Simon's design as described in section 7.4. The interim analysis will be conducted after follow-up data from the first 14 patients will be available after at least 30 days from study inclusion, or otherwise presenting an occurrence of the primary outcomes. The DSMB will consist of 3 members (2 hepatologists and 1 nurse) and an agreed charter by all members will come into operation before the initiation of the study recruitment. To note, this interim futility analysis will have no impact on the type I error at the end of the trial, and thus alpha adjustment is not needed.

The interim analyses will be performed by a statistician of the Medical Statistics core facility independent to the trial design, conduct of the trial and final analysis.

A previous Data Review will be performed before lock of database for the interim analysis. Data Review Meeting with the sponsor in order to carry out the valid population to the interim analysis (according with section 7.4 and 7.5 specifications).

The interim analysis report will be included the conclusions for the observed data according to the stopping roles in section 7.4 and complete list of adverse events characteristics by subject.

7.6 STATISTICAL INTERIM AND MULTIPLICITY ADJUSTMENT

The analysis will follow the principles specified in the ICHE9¹ and the CPMP/EWP/908/99¹² Points to Consider on Multiplicity issues in Clinical Trials guidelines.

The Simon's two-stage optimal design will be conducted in order to futility evaluation for this reason no multiplicity adjustments are needed. All statistical tests will be applied with 0.05 two-sided significant level.

7.7 FLOW CHART OF TRIAL PROCEDURES

Each cycle has 28 days.	Screening ¹	Cycles (+/- 72 hours) (Day 15 only for Cycle 1 and 2)		First radiologic progression	EOT (after last dose +7 days)	Follow-up ²
		Day 1	Day 15			
Demographics	x					
General Informed Consent	x					
Inclusion/Exclusion criteria and Eligibility	x					
Tumor and disease assessments						
Disease assessment by RECIST v1.1 Every 8 weeks from Day 1 Cycle 2 (+/- 7 days)	x					
Fresh tumor biopsy (See section 7.4)	x			x ³		
Study procedures and examinations						
Physical examination	x	x	x	x	x	
ECOG performance status	x	x	x	x	x	
12-lead ECG ⁴	x				x	
Vital signs ⁵	x	x	x	x	x	
Assessment of AEs/SAEs	x	x	x	x	x	
Concomitant medications	x	x	x	x	x	
Diet and gut microbiota	x					
Laboratory tests						
Serum chemistry ⁶	x	x	x	x	x	
Hematology ⁷	x	x	x	x	x	
Coagulation (PT, INR, PTT)	x	x	x	x	x	
HBsAg and HBsAb, HBcAb and HCV Ab; HBeAg and HBeAb, HBV DNA and HDV RNA and HDV Ab(HBV+ subjects only); HCV RNA (HCV+ subjects only)	x				x	
Thyroid function tests (TSH, free T3, free T4)	x					
Urinalysis	x	x	x		x	
Urine or serum pregnancy test (WOCBP)	x					
Other procedures⁸						
Other laboratory blood tests and assays ⁹		x	x Only in C1	x		
Other liver tissue analysis ¹⁰	x			x		
Patient-reported Quality of Life (EQ-5D, EORTC-QLQ C30, EORTC-HCC18 and FACT-Hep) ¹¹		x		x	x	
Other stool tests and assays ¹² Day 1 Cycle 4 and in case of OR or PD		x			x	

EOT: End of Treatment; **OR:** Objective Response; **PD:** Progressive Disease

¹ The time period between study entry and the commencement of protocol treatment is not to exceed 28 days.

² Follow-up visits could be on-site or phone visits after the last visit and will include survival data and liver cirrhosis complications evaluation every 3 months. If the patient does not start any other treatment after end of treatment, radiologic follow-up with the same scheduled will be preferred. Laboratory tests will be performed at the discretion of the treating investigator until death or the end of the study.

³ A biopsy will be performed at the time of progression whenever possible.

⁴ Note: The ECG should be performed within the 7 days prior the randomization. If the QTcF is > 500 ms in first ECG, a total of 3 ECGs should be performed. If the average of these 3 consecutive results for QTcF is ≤ 500 ms, the subject meets eligibility in this regard.

⁵ Including height (only at screening visit) weight, body temperature, respiratory rate, seated blood pressure, heart rate and oxygen saturation (at rest and after mild exercise)

⁶AST, ALT, GGT, Alkaline Phosphatase alkaline phosphatase, Total Bilirubin, Direct Bilirubin, Indirect Bilirubin, Albumin, Creatinine, Alpha alpha fetoprotein, Calcium, Sodium, Potassium, Glucose, Uric Acid, triglycerides, Total Protein, Lipase, Amylase, Magnesium, Phosphate, lactic dehydrogenase LDH, Chloride, Glomerular filtration rate.

⁷Complete blood count with differential

⁸All the samples included in this section, will be centrally analyzed in a second-study

⁹Other laboratory blood tests will include peripheral Blood Mononuclear Cells (PBMCs) immunophenotyping, serum biomarker analysis, polymorphism detection associated with treatment response/resistance, circulating-free DNA analysis, circulating mRNA/miRNA. In case of any cabozantinib dose reduction a blood sample for PBMCs and serum biomarker analysis is recommended but no mandatory. Serum biomarker will be analyzed at each cabozantinib dose reduction. For details see the laboratory manual.

¹⁰Other liver tissue analysis will include tumor and non-tumor infiltrated immune cell population characterization (fresh tissue from biopsy analyzed in situ in each recruiting center) and tumor and non-tumor cell transcriptome analysis (samples can be frozen and stored until analysis). Note that these samples will be obtained accordingly to the time point of “fresh tumor biopsy” but all the analysis will be performed in a second-study.

¹¹Patient-reported Quality of Life (EQ-5D, EORTC-QLQ C30, EORTC-HCC18 and FACT-Hep) will be administered at Day 1 of Cycle 1 and Cycle 3, then at Day 1 every 3 cycle and at end of treatment s.

¹²Other stool tests and assays will include gut microbiota composition and/or metabolomic analysis.

8 STATISTICAL ANALYSIS

8.1 ANALYSIS POPULATIONS

There are only one population for this study:

- Safety Set: All eligible patients who have received at least one dose of Cabozantinib will be included in the Safety population.

The population will be fully defined and documented during the Data Review and before the database lock. The objective will be to carry out the population selection and definition of the final study population.

The Safety population will be used for all analysis including the efficacy secondary endpoints.

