4.1 TREATMENT PLAN

4.1.1 SCREENING PHASE

Study entry is defined as the date that the Informed Consent has been signed by the patient. No patient may undergo any screening procedures that are not considered standard of care to assess his/her eligibility to receive protocol treatment, or commence protocol treatment, prior to signing the informed consent form. The time period between study entry and the commencement of protocol treatment is not to exceed 28 days. Patients may only commence protocol treatment after all eligibility criteria have been confirmed. After signing the informed consent and upon documentation of eligibility, the patient will be allocated with an enrolment number and registered in an enrolment log. The patient identification number will be multi-digit, to represent the investigational site and an enrolment number that will be unique to each subject. All patients referred for possible participation in this study must be assessed at screening to confirm the patient's eligibility. All documentation supports the inclusion and exclusion criteria and screening investigation results are to be retained by the Investigator and made available for monitoring by the study

Sponsor including source data verification. All patients assessed as ineligible to be enrolled in the study after study entry are considered screening failures. The investigator will have their initials recorded on the Patient Screening Log and no further data will be collected for these patients. The Patient Screening Log will include the reason(s) for the patient not meeting the eligibility criteria and will be maintained by the site and copies retained by the study Sponsor. Patient who withdrew consent after study entry but before treatment for any reason will be considered screening failures and should be registered in the screening log.

The study monitor should be contacted in the event of any query or uncertainty relating to a patient's eligibility to receive protocol treatment:

[name]

BCLC group, Liver Unit, Hospital Clinic de Barcelona
Email: [contact]
[contact];
[contact]

[name]

BCLC group, Liver Unit, Hospital Clinic de Barcelona
Email: [contact]
[contact];
[contact]

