9.2 SAMPLE SIZE

The sample size calculation will be triggered by the primary outcome, i.e, the rate of adverse events (AE) with CTCAE \geq 3 excluding palmar-plantar erythrodysthesia (critical AEs). The expected rate for this outcome was 56% in this population¹. The Simon's two-stage optimal design² will be used to test the alternative hypothesis that with cabozantinib the rate of critical AEs will be reduced at least to 32.5% against the null hypothesis of 56% as previously observed. In the first stage, 14 patients will be accrued. If there are 8 or more critical AEs in these 14 patients, the study will be stopped because of futility. Otherwise, 26 additional patients will be accrued for a total of 40. The null hypothesis will be rejected if 23 or fewer critical AEs are observed in 40 patients. This design yields a type I error rate of 2.5% one-sided and power of 80% when the true response rate is 67.5%.

All patients exposed to the study treatment (regardless of protocol adherence) will count be safety, and thus no need to sample size increases as per potential withdrawals are foreseen.

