8.5 STUDY ESTIMAND, HANDLING OF MISSING DATA AND CENSORING RULES

The handling of missing data will follow the principles specified in the ICH-E9 and the CPMP/EWP/1776/99 Rev1¹³. Guideline on Missing Data in confirmatory trials Guidelines. As per the ICH E9(R1) (Addendum on estimands and sensitivity analysis in clinical trials EMA/CHMP/ICH/436221/2017)¹⁴, the plan for the assessment of the Primary endpoint (PEP) (in this study includes the main secondary outcome) is described here after using the 4 attributes of the estimand:

1. Population: as described in protocol and section 8.1 of this SAP, all analyses will be carried out using Safety population.
2. Endpoints: (please see details on the endpoints definitions in section 8.3)
 - a. Non confirmatory primary endpoints (PEPs): the rate and type of:
 - Any AEs
 - Related-AEs
 - Rate of death
 - AEs leading to treatment discontinuation
 - Serious AEs (SAEs)
 - Rate of AEs (CTCAE)≥3 excluding palmar-plantar erythrodysthesia
 - b. Secondary endpoints (SEP):
 - ORR (main secondary outcome)
 - Overall survival (OS)
 - Time to progression (TTP)

- Pattern of progression
- Post-progression survival (PPS)
- Rate of patients who develop new extra-hepatic spread

3. **Intercurrent events (ICEs)**: the relevant intercurrent events expected to occur in this study includes the following situations and the method for handling will be the same for all of them due to the safety characteristics of the primary objective. The “Treatment Policy” strategy will be used, i.e., all observed data will be used regardless of the intercurrent event.

- a. No treatment initiation: exclusion from the analysis.
- b. Main estimand: any other situation regardless of the ICE (use of rescue medication, prohibited concomitant medication, treatment discontinuation, or any reason leading to study discontinuation): “Treatment Policy” strategy (i.e. all observed data will be considered regardless of any previous ICE).
- c. Supplementary estimand: for some relevant efficacy secondary endpoints, data after ICEs will be censored (see table below) and will be based on the while on treatment strategy.

4. **Population-level summary**:

- a. Estimation of rates and 95%CI for the PEPs by means of Clopper-Pearson exact method will be used as the population-level summary (see sections 8.6.5.1 and 8.6.5.2.1).
- b. Time to event variables will be described using the Kaplan-Meier method (see section 8.6.5.2.2).

	Primary Estimand	Supplementary Estimand

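### The SAP's only analysis set is limited to eligible treated patients, while the protocol and the SAP's own sample-size section count everyone exposed

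*SAP*

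**What the plan says.** SAP 8.1 allows one population, used for all analyses including the secondary efficacy endpoints: "All eligible patients who have received at least one dose of Cabozantinib will be included in the Safety population". It then defers the final definition: "The population will be fully defined and documented during the Data Review and before the database lock". SAP 8.6.5.1 applies this set to the primary adverse-event rates.

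Protocol 9.2 takes a wider view: "All patients exposed to the study treatment (regardless of protocol adherence) will count be safety". SAP 7.4 repeats the sentence and draws the planning conclusion from it: "All patients exposed to the study treatment (regardless of protocol adherence) will count be safety, and thus no need to sample size increases".

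SAP 8.5, the estimand section, treats the two sources as one: "as described in protocol and section 8.1 of this SAP, all analyses will be carried out using Safety population". The one exclusion it names is "No treatment initiation: exclusion from the analysis". Every other intercurrent event is handled by treatment policy.

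For the interim, SAP 7.5 has a data review meeting with the sponsor "carry out the valid population to the interim analysis (according with section 7.4 and 7.5 specifications"), so the interim population is tied to the all-exposed wording of 7.4.

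Protocol 4.1.1 sets the safeguard before dosing: "Patients may only commence protocol treatment after all eligibility criteria have been confirmed".

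**The concern.** The two definitions differ by one condition. For a patient who took cabozantinib and was later found not to have met an entry criterion, protocol 9.2 and SAP 7.4 say the patient counts, whereas SAP 8.1 says the patient is outside the only analysis set. No all-treated set exists to fall back on.

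Safety is the primary question, and a severe adverse event in someone who took the drug bears on it directly, whether or not that person should have been enrolled. The trial is open-label and the population is fixed at a data review before lock, so eligibility could be ruled on after the patient's adverse events are known. The interim set follows SAP 7.4 and the final set follows SAP 8.1, so the two Simon decisions could rest on different populations.

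The final decision is a count out of 40, so a single patient can change it. Protocol section 2 and SAP 6.3 make the follow-on exploratory work conditional on meeting the safety endpoint.

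**Working it through.** **1. Passages side by side, for a dosed patient later judged ineligible**

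| Source | Does the patient count? |
|---|---|
| Protocol 9.2, SAP 7.4 | Yes: exposure is enough |
| SAP 8.5 | Not excluded: only non-initiation is listed |
| SAP 8.1, applied by 8.6.5.1 to the primary rates | No: eligibility is also required |
| Protocol 4.1.1 | Eligibility must be confirmed before dosing; no rule for a breach found after dosing |

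**2. Inputs** (protocol 9.2, SAP 7.4). Null critical-event rate p0 = 0.56; alternative p1 = 0.325; 14 patients in stage 1 and 26 in stage 2; stop at 8 or more events of 14; reject the null at 23 or fewer of 40; stated one-sided type I error 2.5% and power 80%.

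**3. Formula.** If the trial continues at c or fewer events in stage 1 and rejects at r or fewer in total,

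P(reject | p) = Σ (x = 0 to c) Bin(x; 14, p) × P(Bin(26, p) ≤ r − x).

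**4. The plan's own figures**

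| Rule | Type I error (p = 0.56) | Power (p = 0.325) |
|---|---|---|
| Printed: c = 7, r = 23 | 0.361 | 0.950 |
| c = 6, r = 16 | 0.0239 | 0.8004 |

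The total of 40 reproduces: the optimal Simon design on the event-free scale (0.44 against 0.675) is 7/14 and 23/40 event-free patients. The printed rule applies those event-free counts to adverse events. In event counts they become continue at 14 − 8 = 6 or fewer and reject at 40 − 24 = 16 or fewer. That mismatch is a separate problem, so both rules are carried forward here.

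**5. One exclusion at the final analysis, starting one event above each cut-off**

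| All exposed | Excluded patient had an event | Excluded patient had no event |
|---|---|---|
| 24/40 = 60.0% | 23/39 = 59.0%; count now 23 | 24/39 = 61.5% |
| 17/40 = 42.5% (95% CI 27.0–59.1) | 16/39 = 41.0% (25.6–57.9); count now 16 | 17/39 = 43.6% (27.8–60.4) |

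Excluding a patient with an event lowers the rate by 60.00 − 58.97 = 1.03 or 42.50 − 41.03 = 1.47 percentage points, and the count meets the cut-off.

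**6. Type I error if k patients are excluded and the cut-off stays the same.** In the worst case every excluded patient had an event, which amounts to rejecting at r + k of 40. In the outcome-neutral case k stage 2 patients are dropped whatever their outcome.

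| Rule | k = 0 | k = 1 worst | k = 1 neutral | k = 2 worst | k = 2 neutral |
|---|---|---|---|---|---|
| c = 6, r = 16 | 0.0239 | 0.0428 | 0.0325 | 0.0692 | 0.0436 |
| Printed, c = 7, r = 23 | 0.361 | 0.391 | 0.381 | 0.409 | 0.397 |

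Check: at p = 0.56 the probability of passing stage 1 with 6 or fewer events and ending at exactly 17 of 40 is 0.0189, which equals 0.0428 − 0.0239.

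The documents do not give k; 1 and 2 are assumptions. At k = 0 nothing changes.

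**The case against.** The best defence is that *eligible* is redundant. Protocol 4.1.1 forbids dosing before eligibility is confirmed and assigns the enrolment number on documented eligibility, so every dosed patient was eligible by procedure. SAP 8.2 uses the word as a step in the patient flow. SAP 7.4, SAP 8.5 and protocol 9.2 all lean towards all-treated, and no passage says a dosed patient may be removed. This is a plausible account of the intent, and it means few patients should be affected. It does not settle the matter. A pre-dose check does not cover a breach found later, for example at the source data verification that 4.1.1 itself provides for, and an entry breach is not an intercurrent event, so 8.5 does not answer it.

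The second line is about size, and much of it stands:

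- The 6/14 and 16/40 cut-offs are not printed in the documents. Under the printed rule one exclusion moves an already failing type I error only from 0.361 to 0.391.
- The 0.0428 and 0.0692 require every excluded patient to have had an event; the neutral figures are 0.0325 and 0.0436. Excluding a patient without an event raises the rate.
- The documents give no rule for 39 patients. A cut-off of 15 of 39 would give 0.017, so inflation is not inevitable.
- SAP 8.6 calls the analysis non-inferential, and a shift of 1.0 to 1.5 points is small beside an interval about 32 points wide (59.1 − 27.0).

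These points limit the magnitude. They do not remove the contradiction, and SAP 7.4 still states a rejection rule.

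**Conclusion.** The concern holds. The SAP gives two answers on whether a treated patient later found ineligible belongs in the primary safety rate, and the restrictive answer sits in the section that defines the only analysis set. Exclusion is possible on that wording; it is not certain.

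The size depends on how many such patients there are and whether they had critical events, and the documents give neither. With none, the effect is zero. With one who had an event, the descriptive rate falls by 1.0 to 1.5 points and the Simon decision can reverse if the count stands one above the cut-off. The type I error figures are illustrations that assume exclusions only at the final analysis and an unchanged cut-off. The planned sample size is not affected. This should be corrected before database lock; it does not by itself invalidate the design.

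**What to change.** In SAP 8.1 remove *eligible* and define the Safety Set as all patients who received at least one dose of cabozantinib, regardless of eligibility or protocol adherence. State that this set serves both the interim and the final Simon decision, so that SAP 7.4, 7.5, 8.1 and 8.5 and protocol 9.2 describe one population. Report entry-criterion breaches among protocol deviations in the existing Table 57. An analysis without those patients may be shown as a sensitivity analysis if wanted.

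The cost is one word deleted and two short statements added. Planned numbers, endpoints, data collection and patient management do not change, and the sensitivity analysis is optional.
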